### 6.1.6 SES-CD

The SES-CD assesses the mucosal appearance of the intestine in subjects with CD [21]. It includes four variables: ulcer size, the extent of ulcerated surface, extent of affected surface, and stenosis.

Each of these four components are assessed in the five segments of the ileum and colon: ileum, right colon, transverse colon, left colon (descending and sigmoid), and rectum. The SES-CD is the sum of the individual scores of each of the components across the five segments. For the SES-CD, a higher score indicates more severe disease.

In addition to obtaining baseline information on the condition of the mucosa, changes in overall mucosal appearance and changes in the SES-CD in response to treatment will be evaluated in an exploratory endoscopy substudy. This substudy will include subjects with a baseline SES-CD  $\geq$ 7 (if ileum and colon are involved) or  $\geq$ 4 (if the lesions are confined to the ileum). These subjects will have an additional ileocolonoscopy at Day 42.

### 6.1.7 Exploratory Efficacy Measures

### 6.2 Safety Assessments

Safety will be monitored during the study as detailed in . Safety variables include evaluations of AEs, laboratory evaluations, vital signs, physical examinations, ECGs and concomitant medications.

#### 6.2.1 Adverse Events

Definition of AE: An AE is any untoward medical occurrence in a subject enrolled in this study (i.e., that occurs after the informed consent form [ICF] is signed), regardless of its causal relationship to study drug.

An AE can therefore be any unfavourable and unintended sign (including a clinically significant abnormal laboratory finding), symptom, or disease.

An AE includes a/an:

- Exacerbation of a pre-existing condition or disease.
- Increase in frequency or intensity of a pre-existing condition.
- Continuous persistent pre-existing disease or symptoms that worsen after the subject provides informed consent.

If a clinically significant abnormal laboratory finding or other abnormal test result meets the definition of an AE or SAE, then the AE eCRF page or SAE eCRF page must be completed, as appropriate. Clinically significant laboratory results include those that:

• Result in discontinuation from the study.

- Require treatment or any other therapeutic intervention.
- Require further diagnostic evaluation (excluding a repetition of the same procedure to confirm the abnormality).
- Are associated with clinical signs or symptoms judged by the Investigator to have a clinically significant impact.

A diagnosis (if known), or clinical signs and symptoms (if diagnosis is unknown), rather than the clinically significant abnormal laboratory finding or test result, should be entered on the AE or SAE eCRF page. If no diagnosis is known and clinical signs and symptoms are not present, then the clinically significant abnormal finding should be recorded as an AE.

An AE does not include a/an:

- Medical or surgical procedure (e.g., surgery, endoscopy, tooth extraction, transfusion); the condition that leads to the procedure is an AE. Any complication of the procedure is also considered to be an AE.
- Pre-existing disease or conditions present or detected at the start of the study that do not worsen.
- Situations where an untoward medical occurrence has not occurred (e.g., hospitalisations for cosmetic elective surgery, social and/or convenience admissions).
- The disease or disorder being studied or sign or symptom associated with the disease or disorder, unless more severe or frequent than expected for the subject's condition.

Any medical condition that is present prior to informed consent should be recorded as medical history and not be reported as an AE.

### Treatment-emergent Adverse Event: A TEAE is defined as

- 1. A new event that occurs during or after treatment with study drug or
- 2. Any event present at Baseline that worsens in either intensity or frequency after exposure to study drug.

#### Definition of Serious Adverse Event:

An SAE, experience or reaction, is any untoward medical occurrence (whether considered to be related to study drug or not), that, at any dose:

- Results in death the death was an outcome of an AE.
- Is life-threatening (the subject is at a risk of death at the time of the event; it does not refer to an event which hypothetically might have caused death if it were more severe).
- Requires inpatient hospitalisation or prolongation of existing hospitalisation: Hospital admissions and/or surgical operations planned before or during a study

are not considered AEs if the illness or disease existed before the subject was enrolled in the study, provided that it did not deteriorate in an unexpected way during the study.

- Results in persistent or significant disability/incapacity, i.e., the AE resulted in a substantial disruption of a person's ability to conduct normal life functions, i.e., the AE resulted in a significant, persistent or permanent change, impairment, damage or disruption in the subject's body function/structure, physical activities and/or quality of life
- Is a congenital abnormality/birth defect in the offspring of a subject who received drug it is suspected that exposure to study drug prior to conception or during pregnancy may have resulted in an adverse outcome in the child.
- Other: Medically significant events, which do not meet any of the criteria above, but may jeopardise the subject and may require medical or surgical intervention to prevent one of the other serious outcomes listed in the definition above. Examples of such events are blood dyscrasias (e.g., neutropenia or anaemia requiring blood transfusion, etc.) or convulsions that do not result in hospitalisation.

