### 4.4 Selection of Study Population

#### 4.4.1 Inclusion Criteria

Subjects who meet these inclusion criteria will be eligible to enrol in the study:

- 1. Male or female subjects aged 18 to 80 years, inclusive at Visit 1
- 2. Willing and able to provide written informed consent
- 3. Willing and able to attend study visits and follow study procedures
- 4. History of Crohn's disease (confirmed by ileocolonoscopy) of at least three months duration prior to Visit 1
- 5. CDAI score of  $\geq$ 220 to  $\leq$ 450 during Screening
- 6. CRP  $\geq$ 5 mg/L (or, if CRP is normal, FCP  $\geq$ 250 µg/g) at Screening
- 7. Active CD of ileum and/or colon as determined by the baseline ileocolonoscopy
- 8. Subjects for the exploratory endoscopy substudy must have a SES-CD  $\geq$ 7 (if ileum and colon are involved) or  $\geq$ 4 (if only the ileum is involved) at the baseline ileocolonoscopy.
- 9. Subject must have failed or experienced intolerance to at least one of the following: aminosalicylates, corticosteroids; immunosuppressants (e.g., azathioprine [AZA], 6-mercaptopurine [6-MP], or methotrexate [MTX]).
- 10. Permitted CD medication regimen expected to remain stable during the period of the study
- 11. Females of childbearing potential must have a negative serum pregnancy test at Visit 1 and agree to use effective contraception from signing informed consent and for at least 90 days after the last dose of study drug. Males who are sexually active with a female partner of childbearing potential must be willing to use effective contraception from signing informed consent and for 90 days after the study.
  - a. Females of childbearing potential include any female who has experienced menarche and who has not undergone successful surgical sterilisation (hysterectomy, bilateral tubal ligation, salpingectomy, or bilateral oophorectomy) or is not postmenopausal. Postmenopausal is defined as no menses for ≥12 months without an alternative medical cause. Females with questionable menopausal history (e.g., irregular menstrual periods and age >40 years) are considered to be of childbearing potential.
  - b. Females of childbearing potential: Females of childbearing potential must use acceptable highly effective (according to Clinical Trial Facilitation Group [CTFG] recommendations) methods of birth control in this study. These include:

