#### 4.4.2 Exclusion Criteria

Subjects who meet any of these criteria are not eligible to enrol in this study.

- 1. Crohn's disease of mouth, oesophagus, stomach or duodenum which, in the opinion of the Investigator, is likely to be causing symptoms
- 2. Known history of or suspicion of ulcerative colitis, indeterminate colitis, microscopic colitis, ischaemic colitis or radiation-induced colitis, based on medical history, endoscopy and/or histological findings
- 3. Any GI manifestations of CD that might affect the evaluation of efficacy:
  - a. Prior significant GI resection
  - b. Current abscess or symptomatic stricture
  - c. Abdominal, enterocutaneous or pelvic active fistulas or fistula likely to require surgery during the study. Non active/non draining fistulas (including seton drained fistulas) are allowed.
  - d. History of short bowel syndrome
  - e. Presence of ileostomy or colostomy
- 4. Isolated disease confined to the recto-sigmoid colon (approximately the last 25 cm)
- 5. Any abdominal surgery within the six months before Visit 1 that required entering peritoneal cavity
- 6. Planned surgery or likely need for surgery during the study period
- 7. Any history of GI tract dysplasia or neoplasia
- 8. Any history of lymphoproliferative disease
- 9. Required enteral or parenteral feeding within 6 months before Visit 1 (oral supplements are acceptable)

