### 4.5 Subject Withdrawal

All subjects are free to withdraw from participation in the study at any time, for any reason, specified or unspecified, and without prejudice to further treatment. In addition, subjects will be withdrawn from study drug and from the study in the following circumstances:

- The Investigator decides that the subject should be withdrawn. If this decision is made because of an intolerable AE or a clinically significant laboratory value, the study drug is to be discontinued and appropriate measures are to be taken. The Medical Monitor is to be notified immediately.
- The subject is unwilling to continue in the study.
- Noncompliance or protocol violations that in the opinion of the Investigator or Sponsor/designee necessitates the subject being removed. The decision to withdraw the subject should be taken in consultation with the Medical Monitor.
- Pregnancy
- Events that require emergency unblinding
- Has infectious complications that require stopping or reduction of immunosuppressive therapy

- Requires any abdominal surgery or surgery for fistula or abscesses; the decision to withdraw the subject should be taken in consultation with the Medical Monitor.
- The Investigator or the Sponsor, for any reason, stops the study.

In general, before the decision is made to withdraw the subject, consultation with the Medical Monitor is recommended.

If a subject chooses to withdraw from the study (permanently stop taking the study drug), they will be encouraged to return to the site for safety reasons to complete the assessments planned for Visit 5 (Day 42) during an Early Termination Visit and for the Follow-up Visit (Day 56).

The Investigator should ensure that all reasonable attempts (telephone calls, contact with primary care physician, certified letter) are made to obtain follow-up safety information on subjects who do not return to the site for study visits or are lost to follow-up.

Subjects who are withdrawn from the study after randomisation and who receive at least one dose of study drug will not be replaced. These subjects cannot be rescreened.

Subjects who withdraw from the study after dosing should be advised by the Investigator to continue contraception restrictions for 90 days after the last administration of study drug.

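### The SAE definition lets a Crohn's admission or operation planned after consent be left out as an expected deterioration, in conflict with the protocol's other AE rules

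*Protocol*

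**What the plan says.** The hospitalisation criterion in the Protocol's definition of a serious adverse event carries an exemption. It covers "Hospital admissions and/or surgical operations planned before or during a study". These "are not considered AEs if the illness or disease existed before the subject was enrolled in the study". A proviso limits the exemption to illness that has not worsened unexpectedly: "provided that it did not deteriorate in an unexpected way during the study". Something that is not an AE cannot be an SAE.

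The general AE definition in Section 6.2.1 has rules that point in both directions:

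- **Towards reporting.** An AE includes "Exacerbation of a pre-existing condition or disease" and persistent pre-existing disease that worsens after consent. A procedure is not itself an AE, but the condition that led to it is. Section 6.2.1.1 repeats this last rule.
- **Away from reporting.** An AE does not include "The disease or disorder being studied or sign or symptom associated with the disease or disorder, unless more severe or frequent than expected"; the sentence goes on to set that test by the subject's own condition. The list closes by sending any condition present before consent to medical history, with no qualifier for worsening.

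Exclusion criterion 6 is "Planned surgery or likely need for surgery during the study period". Section 4.5 nevertheless foresees operations on study, since a subject is withdrawn who "Requires any abdominal surgery or surgery for fistula or abscesses".

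**The concern.** An exemption of this kind normally keeps elective procedures arranged before the trial out of the SAE count. Adding *or during* extends it to admissions and operations arranged once the subject is on study drug. In a Crohn's disease trial these are among the events a safety review most needs to see, because they may show that treatment has failed or that the disease has worsened.

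If some sites use the exemption and others follow the opposing rules, the SAE count depends partly on local reading. Expedited reporting depends on the same definition. SAP Section 4.1 plans no data monitoring committee and Protocol Section 8.3 plans no interim safety analysis, so neither would pick up inconsistent classification during the trial.

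**Working it through.** The plan states no figure on this point, so the check is mainly a reading of the rules against each other.

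1. **First condition: the illness predates enrolment.** Inclusion criterion 4 requires "History of Crohn's disease (confirmed by ileocolonoscopy) of at least three months duration prior to Visit 1". For Crohn's disease this condition is met in every eligible subject and filters nothing.

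2. **What *before* and *during* each reach.** Exclusion 6 removes subjects whose surgery is planned or likely at entry. A Crohn's operation on study would therefore normally have been decided after entry. For such operations *before* has little to act on, and *during* does most of the work.

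3. **Second condition: no unexpected deterioration.** The Protocol defines unexpectedness only for adverse drug reactions, against the Investigator's Brochure. It gives no definition for the course of a disease. Section 2.1 describes Crohn's disease as relapsing and progressive, and says that about half of patients have an intestinal complication within 20 years, often leading to surgery. An investigator could read that as making a deterioration expected.

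4. **One event, two classifications.** Suppose that between Day 14 and Day 42 an investigator plans an inpatient operation because a subject's Crohn's disease has worsened.
   - Under the rules on exacerbation and on the condition behind a procedure, the worsening is an AE. Inpatient hospitalisation makes it serious, so it goes into a 24-hour report (Section 6.2.1.3) and the serious-TEAE table.
   - Under the exemption, if the worsening is judged expected, the admission and operation are not AEs. The studied-disease rule can then be used to exempt the underlying Crohn's disease as well. Nothing is reported as serious.

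   The Protocol does not say which rule prevails.

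5. **What reaches the tables.** Protocol Section 8.2.5.1 summarises only TEAEs. SAP Section 17.1.3 takes SAEs from events marked serious on the AE page. An event classified the second way is absent from the serious-TEAE table and from the table of TEAEs leading to discontinuation (SAP Section 17.1.2). SAP Section 9 still tabulates early discontinuation and its primary reason by arm, so a withdrawn subject remains visible there, but without severity, seriousness or relatedness.

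6. **Scale.** Section 5.6 plans 84 subjects on V565 and 42 on placebo. If all are dosed, one missed subject changes SAE incidence by:
   - V565: 1/84 = 1.2 percentage points
   - placebo: 1/42 = 2.4 percentage points

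   The documents give no rate of Crohn's admission or surgery. Under an assumed 1% to 5%, the total would be 126 × 0.01 = 1.3 to 126 × 0.05 = 6.3 subjects. That is a ceiling for each assumed rate, because only events that are both planned and judged expected could be exempted.

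**The case against.** The strongest reply is that the Protocol, read as a whole, already makes these events reportable. The condition behind a procedure is an AE, and this is said twice. Worsening after consent is an AE. The studied-disease rule is set by the individual subject's condition, not by what is usual in Crohn's disease. Exclusion 6 also cuts the other way: if surgery was judged unlikely at entry, a deterioration that requires it weeks later is naturally unexpected for that subject, and the proviso keeps it reportable. Exclusions 3b and 3c, which bar current abscess, symptomatic stricture and active fistula of the listed types, support the same reading.

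Much of this stands. It shows that reporting is a reasonable reading, and perhaps the better one. It does not show that it is the only one, because expectedness is left to judgement and no order of precedence is given.

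A reader might infer more than the text supports:

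- **That a subject withdrawn for surgery will have no AE or SAE.** The opposing rules forbid that conclusion; it is one of two available classifications.
- **That all Crohn's admissions are exempt.** The exemption is limited to what is planned, and an emergency admission is not plainly covered. The separate studied-disease rule could still be argued there.
- **That the events vanish altogether.** Withdrawals and their reasons are tabulated.
- **That a large share of all SAEs would be lost.** The documents give neither a total SAE count nor a rate of Crohn's admission or surgery.

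**Conclusion.** The point holds as an internal conflict in the safety definitions. The SAE exemption lets an investigator leave out a Crohn's admission or operation planned after consent by judging the deterioration expected, while Sections 6.2.1 and 6.2.1.1 would have the underlying condition recorded as an AE. The 24-hour reports and the serious-TEAE table may therefore understate such events.

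The conclusion rests on the wording alone and needs no assumption about rates. How many events are affected, and in which arm, cannot be determined from the documents. The only firm measure of size is the weight of a single missed subject: 1.2 points on V565 or 2.4 on placebo, assuming the planned arm sizes are reached and all subjects are dosed. The correction is worth making because it is cheap and protects safety reporting.

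**What to change.** Three changes to the Protocol's reporting text:

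1. In the SAE definition, delete *or during*, so that only admissions or operations planned before informed consent are exempt.
2. Add that the condition leading to any Crohn's admission or operation decided on after consent is recorded as an AE and judged against the seriousness criteria. This agrees with the procedure rule in Sections 6.2.1 and 6.2.1.1.
3. State in Section 6.2.1 that the studied-disease exemption does not override item 2.

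The change should stop there. Making every departure from baseline Crohn's symptoms an AE would largely duplicate the CDAI and PRO-2 data and add many non-serious reports. Little is lost by item 1, because Section 6.2.1 already says that pre-existing conditions that do not worsen are not AEs.

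The cost is a wording amendment, a memo to sites and a few more SAE reports. The analysis is unchanged.

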### Other Adverse Event Definitions:

An Adverse Drug Reaction (ADR) is defined as all noxious and unintended responses to a medicinal product related to any dose.

An Unexpected ADR is defined as any adverse reaction, the nature of which is not consistent with the applicable product information and is unexpected. An adverse reaction is 'unexpected' if its nature and severity are not consistent with the information about the medicinal product in question set out in Section 7 of the IB.

A Suspected Unexpected Serious Adverse Reaction (SUSAR) is an adverse reaction, the nature or severity of which is not consistent with the applicable product information (e.g., for applicable product information, include the IB for an unapproved investigational product or the package insert/summary of product characteristics for an approved product). Therefore, if a treatment-related SAE occurs and it was not mentioned in the applicable product information, then it will be reported as a SUSAR.

#### Definitions of Severity

The severity of the AE will be characterised as "mild, moderate or severe" according to the following definitions:

- Mild events are usually transient and do not interfere with the subject's daily activities.
- Moderate events introduce a low level of inconvenience or concern to the subject and may interfere with daily activities.
- Severe events interrupt the subject's usual daily activity.

#### Definitions of Relationship

Causal relationship must be assessed by the Investigator answering the following question:

'Is there a reasonable possibility that the drug caused the event?'

- Yes There is a reasonable or strong temporal relationship, and the events are unlikely attributed to other drugs, underlying diseases or other factors.
- No There is no strong temporal relationship, and/or use of other drugs, underlying diseases, or other factors provide plausible explanations for the occurrence of the event.

#### 6.2.1.1 Monitoring of Adverse Events

The Investigator is responsible for recording all AEs observed during the study (screening, treatment, and follow-up periods). At each visit, the subject will be asked if they have experienced any untoward occurrence since the last trial visit. In addition, subjects will be instructed to contact the study site at any time after the ICF is signed if any symptoms develop.

All AEs/SAEs should be recorded individually in the study subject's own words (verbatim) unless, in the opinion of the Investigator, the AEs/SAEs constitute components of a recognised condition, disease, or symptom. The Investigator should attempt to establish a diagnosis of the event based on signs, symptoms, and/or other clinical information. In such cases, the diagnosis should be documented as the AE and/or SAE rather than the individual signs/symptoms.

All AEs will be recorded on the eCRFs and include a description of the event, severity, time of occurrence, and duration. In addition, any action (e.g., treatment and follow-up tests) and the outcome should be provided along with the Investigator's assessment of the relationship to the investigational drug.

In cases of surgical or diagnostic procedures, the condition/illness leading to such a procedure is considered as the AE rather than the procedure itself.

In cases in which the subject dies, the cause of death should be recorded as an SAE; death is considered the outcome of the SAE.

Adverse events should be followed until recovery to the normal state has been achieved. In the event of a subject not returning to the study site, the outcome of this event will be recorded as unknown.

